### **2.4.1.3 Sample Size**

On the basis of unpublished data, a 14% response rate was assumed for the sham acupuncture group in this study. We estimated that a sample size of 100 participants would provide 90% power to detect a between-group difference of 31.4% at the two-sided significance level of 0.05 and 20% loss to follow-up.

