### 2.4.2.1 Inclusion Criteria

(1) Cancer patients must meet the Rome IV diagnostic criteria for OIC. Participants have at least 2 of the following new or worsening symptoms of constipation following initiation, alteration, or increase in opioid treatment: fewer than three SBMs per week, straining (>25% of defecations), sensation of incomplete evacuation (>25% of defecations), lumpy or hard stools (>25% of defecations), and/or sensation of anorectal obstruction/blockage (>25% of defecations). For patients with a history of chronic functional constipation, he/she must have worsening symptoms of constipation when the opioid therapy is initiated, changed, or the dose is increased; (2) Patients recruited in this trial must have a history of OIC symptoms for at least 1 week; (3) Patients must be  $\geq 18$ years of age and ≤85 years of age; (4) Patient's cancer condition must be stable with a life expectancy that is more than six months; (5)Patients must have an Eastern Cooperative Oncology Group (ECOG) performance status of 0-3; (6) Patients must have been receiving a stably maintained opioid regimen, consisting of a total daily dose of 30 mg to 1000 mg oral morphine equivalents for at least 2 weeks prior to screening for cancer pain. Furthermore, it must be anticipated that the opioid will be maintained for at least 10 weeks; (7) The SBM frequency of the patients must be 2 times a week when laxatives are not being taken: (8) Patients must be capable of oral intake of drugs, food and beverages; (9)Provision of written informed consent before inclusion.

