### 7.6 Data Auditing

When the data checking is finished, a data auditing and blinding review meeting will be hold. On the meeting, the data administrators, statisticians, researchers, clinical inspectors, and other related members would have a discussion on the following items according to the data management report and the data lists:

- Distribution of the participants;
- Protocol disobeying or not;
- Possible outlier;
- Baseline data;
- Outcomes;
- Statistical analysis plan.

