### 8. Statistical Consideration

The following is an overview of the statistical considerations. Details of the pre-specified statistical analyses can be found in the Statistical Analysis Plan (SAP).

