### 8.2 Statistical Analysis Plan (SAP)

Prior to database lock and before code breaking, a final version of the SAP shall be issued and approved by the study statistician, and the principal investigator. The SAP will define all "pre-specified, planned analyses" and provide the general specifications for the analysis of the data to be collected and presented in the Clinical Study Report.

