4.4.3 Analyses for Primary Outcome

The primary outcome will use a generalized linear model with a binomial distribution and identity link. The subgroup analysis will be conducted by adding an interaction between the baseline daily opioid dose and treatment into the generalized linear model

As a sensitivity analysis, missing data on the primary outcome will be imputed using the multiple imputation method under the missing at random assumption.

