4.4.5 Safety Analyses

All adverse events and serious adverse events will be listed. Adverse events include the acupuncture-related adverse events and other adverse events.

5. The Summary of Changes of Final SAP

As compared to the original statistical analysis plan (SAP) published in the *Front. Med.* ([name], [name], [name], et al. Effects of Electroacupuncture on Opioid-Induced Constipation in Patients with Cancer: Study Protocol for a Multicenter Randomized Controlled Trial. Front Med. 2022), the present finalized SAP had made a few amendments. The major updates were provided in Table 1.

Table 1. MAJOR UPDATES OF THE ORIGINAL SAP

No.	Item	Original Version	Final Version
1	Missing	Missing data on the primary	As a sensitivity analysis, missing
	data	outcome will be imputed using	data on the primary outcome will be
		the multiple imputation method	imputed using the multiple
		under the missing at random	imputation method under the
		assumption.	missing at random assumption.
2	Primary	The primary outcome will be	The primary outcome will use a
	outcome	evaluated using the x^2 test.	generalized linear model with a
			binomial distribution and identity
			link.
3	Safety	AE incidences for each	AE data will be provided for
	outcome	treatment group will be	descriptive purposes only.
		compared using Fisher's exact	-
		test.

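### Does SAP 4.4.3 need to fix the coding of opioid dose before its dose-by-treatment analysis can be used?

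*SAP*

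**What the plan says.** The primary analysis is given in SAP 4.4.3: "The primary outcome will use a generalized linear model with a binomial distribution and identity link". The next sentence adds the only effect-modification analysis in either document: "The subgroup analysis will be conducted by adding an interaction between the baseline daily opioid dose and treatment into the generalized linear model". Nothing is said about the scale of dose, any cut-point, the interaction test, or what to do if the model fails to converge.

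Protocol 8.1 does not mention a subgroup analysis. Protocol 8 defers to the SAP: "Details of the pre-specified statistical analyses can be found in the Statistical Analysis Plan (SAP". SAP section 5 describes itself as final: "the present finalized SAP had made a few amendments". The one fact given about dose is the eligibility criterion in protocol 2.4.2.1, a stable regimen "consisting of a total daily dose of 30 mg to 1000 mg oral morphine equivalents". For expected response, protocol 2.4.1.3 states that "a 14% response rate was assumed for the sham acupuncture group in this study", with a difference of 31.4 points to be detected.

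Two procedural steps come before unblinding. Under protocol 7.6, "a data auditing and blinding review meeting will be hold", and its agenda includes the SAP. Under protocol 8.2, "Prior to database lock and before code breaking, a final version of the SAP shall be issued".

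**The concern.** With an identity link and continuous dose, each arm's response probability is a straight line in dose that must stay between 0 and 1 at every observed dose. Eligible dose spans a 33-fold range (1000/30). The sham arm expects only about 7 responders (0.14 × 50), so a chance slope can easily push its line to zero at one end. In such a boundary fit the usual standard error no longer has its normal meaning.

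The worry is that the trial's only test of effect modification could report a dose interaction that is not there, or fail to converge. An analyst could also choose the coding after seeing results. The primary analysis was changed from a chi-square test to the identity-link model (SAP section 5, Table 1), and that change is what brings the range constraint into the interaction model.

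**Working it through.** **Inputs.** Protocol 2.4.1.3: sham 14%; EA 14 + 31.4 = 45.4%; two-sided 0.05; 90% power; 20% loss; N = 100. Protocol 2.4.1.1: 1:1 allocation, hence 50 per arm, or 40 after loss. Protocol 2.4.2.1: dose 30–1000 mg/day. The documents give no dose distribution, so the distributions below are assumptions.

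**The plan's own figure.** Unpooled two-proportion formula: n = (1.960 + 1.282)² × (0.14×0.86 + 0.454×0.546) / 0.314² = 10.51 × 0.3683 / 0.0986 = 39.2, so 40 per arm. Then 40/0.8 = 50 per arm, and the stated 100 is reproduced.

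**Primary model.** With treatment alone, a sham boundary needs no responders among 50: 0.86⁵⁰ = 0.0005. The primary analysis is not at risk.

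**Continuous dose: how often is the fit on the boundary?** Treatment, dose and their product amount to one line per arm. Constrained maximum likelihood, 2000 simulated trials per setting, no true dose effect; percentage with either arm on the boundary:

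| Assumed dose distribution | mg, 50/arm | mg, 40/arm | log dose, 50/arm | log dose, 40/arm |
|---|---|---|---|---|
| Uniform 30–1000 | 22.2 | 29.6 | 34.8 | 41.7 |
| Uniform 30–300 | 23.2 | 30.5 | 29.2 | 35.8 |
| Log-uniform 30–1000 | 30.1 | 37.4 | 21.7 | 29.8 |
| Log-uniform 30–300 | 26.2 | 34.6 | 21.2 | 29.4 |
| Lognormal, median 80, log-SD 0.6 | 47.4 | 53.3 | 32.6 | 42.1 |
| Lognormal, median 80, log-SD 0.9 | 53.7 | 57.5 | 30.6 | 41.1 |
| Normal, mean 100, SD 20 | 37.3 | 43.2 | 40.0 | 45.0 |

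The last three are truncated to 30–1000. At 50 per arm the range is 21–54%, mostly from the sham arm.

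**Does that produce false interactions?** It depends on the test. Rejection at nominal 5%, 50 per arm, all fits, across simulations with several of these distributions and both dose scales:

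| Interaction test | Rejects |
|---|---|
| Wald, expected information | 7–19% |
| Wald, observed information | 2–5% |
| Likelihood ratio | 5–7% |

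The weights explain the gap. Expected information weights a patient by 1/[p(1−p)]: at p = 0.14 this is 1/0.1204 = 8.3, but at a near-boundary p = 0.001 it is 1/0.000999 = 1001. A few patients at the end of the dose range then shrink the standard error artificially. Observed information for a non-responder is 1/(1−p)², which at p = 0.001 is only 1.002. How SAS 9.4 reports such fits was not tested.

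**Two even dose groups.** With 25 sham patients per group, the chance that a given group has no responder is 0.86²⁵ = 0.023; for either group, 1 − (1 − 0.023)² = 0.046. Allowing for uneven division of the arms at a pooled median gives 4.9%. At 20 per group, 0.86²⁰ = 0.049 and 1 − (1 − 0.049)² = 0.096, or 10.1% with uneven division. Wald interaction rejection is 5.9% at 50 per arm and 6.2% at 40; with score-based intervals it is 5.0% and 4.9%.

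**Would prescribing a split gain anything?** Take an assumed true interaction, with EA response falling from 65% to 26% across dose and sham flat. A median split detects it in 23–25% of trials. Continuous dose detects it in 34–38% with the expected-information Wald test, a figure inflated by that test's false rejections, and in about 19–30% with a likelihood-ratio test. No coding is clearly better, and all have low power.

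**The case for a change.** The omission is real. Two analysts could read SAP 4.4.3 and fit different models, in a SAP that calls itself final and to which the protocol hands the detail. Boundary fits under continuous dose are frequent on any distribution tried, and more so after 20% loss (29–58%). The likelihood-ratio test is no complete cure: within boundary fits alone it still rejects in 8–14%. Grouping is not automatically safe either. Tertiles leave an empty or full cell in 23–27% of trials at 50 per arm, and a 20:80 cut does so in 24–25%. One or two sentences would remove the ambiguity, and the blinded review is not obliged to supply them.

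The ambiguity and the boundary frequency stand. What does not stand is the inference that the plan carries an inflated error rate. That inflation belongs to one variance formula, which the SAP does not prescribe, and over all fits the other two tests are near or below nominal. The headline frequency also applies only to continuous dose, whereas calling the analysis a subgroup analysis points to groups. Mandating a median split with score-based intervals would swap one debatable choice for another, since it discards dose information and replaces the specified model's own inference.

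**Conclusion.** No change to the plan is called for. SAP 4.4.3 leaves out the dose coding, the interaction test and a fallback. These are details that an analyst would ordinarily settle, and the blinded review and the final SAP before code breaking give the occasion to do so. Under the natural reading, two roughly even groups, the problem is small: about a 5% chance of an empty or full cell (10% at 40 per arm) and 5.9% rejection at nominal 5%. Under continuous dose, boundary fits are common (21–54% at 50 per arm), but overall false rejection stays near or below nominal unless an expected-information Wald test is used.

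The analysis has low power however dose is coded, no stated decision depends on it, and the primary treatment comparison is unaffected. These figures rest on the planned 14% and 45.4%, on assumed dose distributions within the eligible range and, for the error rates, on no true dose effect. A true dose effect would make boundary fits more frequent under continuous dose (37–84% in the settings tried), but would not touch the primary result.

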4.4.4 Analyses for Secondary Outcomes

Efficacy analyses for all secondary outcomes will be performed in the ITT population, without imputation of missing data.

Continuous data will be described with the average, standard deviation, median, minimum value, and maximum value, whereas categorical data will be represented by percentages as appropriate.

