### 2.4.1.1 Randomization

Web-based central randomization will be performed by the Linkermed Pharm Technology Co. Ltd (Beijing, China). Participants will be randomly allocated, in a 1:1 ratio, to either the EA or the SA group using permuted block-randomization. Acupuncturists in each center will be responsible for getting random numbers. Via inputting the screening information of the participant in the central randomization system through the web, they will get the random number and group allocation.

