- (8) A change in the mean score for the straining of SBMs from the baseline during weeks 1-8 and weeks 13-16. For assessment of the straining of SBMs, each patient will be asked to rate his/her score of straining, using the following five-point scale: not at all difficult (0), a little bit difficult (1), moderately difficult (2), quite a bit difficult (3), extremely difficult (4). Assessment time frame: baseline, over weeks 1-8 and 13-16.
  - (9)A change in the total and subscale score of the Patient Assessment of

Constipation-Symptom (PAC-SYM) questionnaire from the baseline at weeks 8 and 16. The PAC-SYM is a questionnaire used to evaluate the severity of chronic constipation in the past 2 weeks. It consists of 12 items, which are subdivided into abdominal (4 items), rectal (3 items), and stool (5 items) scales.34 36 The score of each item ranges from 0 to 4, with 0 = symptom absent, 1 = mild, 2 = moderate, 3 = severe and 4 = very severe. Lower scores indicate a lower symptom burden. Each subscale score will be calculated as the mean of the completed items for that subscale. The total score will be calculated as the mean of all completed items. In this trial, the Chinese version of PAC-SYM, which has been validated to have a satisfactory psychometric property, will be used. Assessment time frame: at baseline, at weeks 8 and 16.

- (10) A change in the total and subscale scores of the Patient Assessment of Constipation-Quality of Life (PAC-QOL) questionnaires from the baseline at weeks 8 and 16. The PAC-QOL is a 28-item self-reported questionnaire to assess the burden of constipation on patients' everyday functioning and well-being in the 2 weeks (14 days) prior to assessment. This questionnaire is divided into four subscales: physical discomfort (items 1-4), psychosocial discomfort (items 5-12), worries/concerns (items 13-23), and satisfaction (items 24 to 28). Each of the item scores ranges from 0 (not at all) to 4 (extreme), with lower scores indicating a better quality of life. For each visit, individual subscale scores will be calculated as the mean of the completed items for that subscale. The total score will be calculated as the mean of all of the completed items. We will use the Chinese version of this test in our trial, which has been demonstrated to be a reliable and valid tool. Assessment time frame: at baseline, at weeks 8 and 16.

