### 8.1 Statistical Analysis

The primary study hypothesis is that EA is more effective than SA in the treatment of OIC in patients with cancer. The primary outcome is the proportion of responders, defined as a patient that has  $\geq 3$  SBMs/wk and  $\geq$  increase of 1 SBM from baseline simultaneously for at least 6 out of 8 weeks of the treatment period. The primary analysis will be intention-to-treat, which is defined as all randomized participants.

The following secondary outcomes will be analyzed using the t test, repeated measures analysis, Wilcoxon rank-sum test, Chi-square test or Fisher's exact test, as appropriate: A two-side test with p<0.05 will be considered significant for all analyses.

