4.4 Statistical Analyses

4.4.1 The General Principle

Summary tables (descriptive statistics and/or frequency tables) will be provided for all variables at different endpoints. For continuous variables, means and standard deviations will be presented, unless the variable has a skewed distribution, in which case medians, 25th and 75th percentiles will be presented. For categorical variables, the number and percentage of participants within each category will be presented. For each variable (continuous or categorical), the number of missing values will be reported.

Statistical Comparisons Between Groups

Continuous variables will be compared using a two-sample *t*-test or Wilcoxon rank-sum test if data show serious deviations from a normal distribution. Categorical data or ordinal data will be compared using a Wilcoxon rank-sum test, chi-square test or Fisher's exact test, as appropriate. All tests will be two-sided.

For the analysis of the primary and secondary outcomes, estimated treatment differences and associated 95% two-sided confidence intervals will be presented.

Analysis Software

For all statistical analyses, SAS 9.4 software will be used. All hypothesis testing will be carried out at the 5% (2-sided) significance level.

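### The SAP names no repeated-measures model for PAC-SYM and PAC-QOL, so as written a patient with a week-8 but no week-16 score is left out of the week-16 comparison

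*SAP*

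**What the plan says.** Protocol 2.4.4.2, items (9) and (10), defines the outcomes as changes in total and subscale scores; for PAC-QOL the wording is "questionnaires from the baseline at weeks 8 and 16", and PAC-SYM has the same visits. Each patient can therefore contribute two post-baseline scores.

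Protocol 8.1 says secondary outcomes will be analysed "using the t test, repeated measures analysis, Wilcoxon rank-sum test", chi-square or Fisher's exact test, as appropriate. It does not say which outcome gets which method, which repeated-measures model is meant, or how incomplete patients are handled. Section 8 of the protocol sends the reader to the SAP for details.

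SAP 4.4.1 compares continuous variables with a two-sample t-test, or a "Wilcoxon rank-sum test if data show serious deviations from a normal distribution". SAP 4.4.4 adds: "Efficacy analyses for all secondary outcomes will be performed in the ITT population, without imputation of missing data". It names no longitudinal model. SAP 4.3 bases all analyses on the randomised set. SAP 4.4.3 limits multiple imputation to a sensitivity analysis of the primary outcome.

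**The concern.** A two-sample test on the week-16 change cannot use a patient who has no week-16 value. With nothing imputed and no model linking the visits, that patient's week-8 score plays no part at week 16. The all-randomised label in SAP 4.3 and the method in 4.4.1 and 4.4.4 cannot then both hold at that visit.

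Loss related to earlier symptoms is plausible here. The patients have cancer, week 16 falls 8 weeks after treatment ends, and Protocol 2.4.2.3 gives worsening symptoms as a ground for withdrawal. If loss after week 8 depends on the week-8 score differently in the two arms, the week-16 difference in symptoms and quality of life is biased. If loss is missing at random given the week-8 score, the trial already collects what is needed to correct this.

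**Working it through.** **Inputs from the documents.** Protocol 2.4.1.3 says that "a sample size of 100 participants would provide 90% power to detect a between-group difference of 31.4" percentage points, that "a 14% response rate was assumed for the sham acupuncture group in this study", and sets a "two-sided significance level of 0.05 and 20% loss to follow-up". Allocation is 1:1 (2.4.1.1). No power is stated for PAC-SYM or PAC-QOL.

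**Step 1: the plan's own figure.** With 14% against 14 + 31.4 = 45.4%, the unpooled formula gives n = (0.14×0.86 + 0.454×0.546) × (1.960 + 1.282)² / 0.314² = 0.3683 × 10.507 / 0.0986 = 39.2, so 40 per arm. Then 40/0.80 = 50 per arm, 100 in total. The stated size reproduces, and 20% loss means 50 falling to 40 per arm.

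**Step 2: assumptions not in the documents.** The change scores have SD 1 at each visit and a true arm difference of 0.50 SD. The correlation ρ between weeks 8 and 16 is 0.5 to 0.7. Total loss by week 16 is 20% in each arm. Where loss depends on the week-8 score, patients doing worse leave more often, with log-odds k = 0.5 to 1.5 per SD.

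**Step 3: bias of the available-case difference at week 16.** Let δ be the shift in an arm's mean week-8 score, in SD, caused by keeping only those who stay. That arm's week-16 mean is off by ρδ. If δ is the same in both arms, the errors cancel and the bias is about 0. If it arises in one arm only, the bias is ρδ. Integrating the logistic loss probability over a normal week-8 score gives:

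| Timing of loss | k | δ | Bias, ρ = 0.5 | Bias, ρ = 0.7 |
|---|---|---|---|---|
| All after week 8 | 0.5 | 0.096 | 0.048 | 0.067 |
| All after week 8 | 1.0 | 0.173 | 0.087 | 0.121 |
| All after week 8 | 1.5 | 0.227 | 0.113 | 0.159 |
| Half before week 8, at random | 0.5 | 0.054 | 0.027 | 0.038 |
| Half before week 8, at random | 1.0 | 0.100 | 0.050 | 0.070 |
| Half before week 8, at random | 1.5 | 0.134 | 0.067 | 0.094 |

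In the lower rows, 10% leave before week 8 and 10/90 = 11.1% of the rest leave after it. If the sham arm loses its poor responders, the estimate falls from 0.50 to between 0.45 and 0.34 SD (upper rows) or between 0.47 and 0.41 SD (lower rows). If the electroacupuncture arm loses them, the sign reverses. Simulation of the upper rows agrees: available-case estimates run from 0.450 down to 0.341, while an estimator that uses the week-8 scores stays at 0.497 to 0.502.

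**Step 4: precision under random loss.** The available-case SE is √(2/40) = 0.224. Using week 8, it is √(2[(1−ρ²)/40 + ρ²/50]). This equals √0.0475 = 0.218 for ρ = 0.5 and √0.0451 = 0.212 for ρ = 0.7, a reduction of 2.5% to 5.0%. If half the loss comes before week 8, replace 50 by 45; the reduction is then 1.4% to 2.8%.

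**The case against.** A reader might infer that the plan has settled on visit-by-visit tests in patients with data, or that the SAP rules out anything else. The documents do not support that. Protocol 8.1 lists repeated measures analysis, SAP 4.4.1 is headed as a general principle, SAP 4.4.4 names no test, and the SAP's table of major updates does not record dropping repeated measures. A likelihood-based mixed model imputes nothing, so it fits SAP 4.4.4 as worded. This stands, and it makes the point a gap in specification. It does not close the gap: the only tests the SAP names for continuous data are two-sample tests, the protocol defers to the SAP, and a classical repeated-measures ANOVA would also drop incomplete patients.

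A reader might also extend the point to week 8. That fails, because week 8 is the first post-baseline visit for these scores and there is no earlier one to discard.

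The size is open to challenge too. Loss that depends on symptoms in one arm only is a chosen scenario; equal dependence gives almost no bias. The 20% loss carries no timing and was set for an outcome measured over weeks 1 to 8, so much of it may come before any week-8 score exists. Both objections stand, which is why the results are shown as a range. Finally, the SAP openly says nothing is imputed and will report missing counts for each variable. That helps a reader see the problem but does not remove it.

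**Conclusion.** The concern holds as a gap between the two documents. As the SAP is written, the week-16 PAC-SYM and PAC-QOL comparisons omit patients whose week-8 score is known, and so are available-case. Under the assumptions in the working, the bias is about 0 with equal dependence in both arms. With dependence in one arm only, it is about 0.05 to 0.16 SD if all loss follows week 8, and about 0.03 to 0.09 SD if half precedes it. The gain in precision is small, so the case for change rests mainly on protection against loss that differs by arm.

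It would go too far to conclude that the week-16 results will be biased: the documents do not say how loss will depend on symptoms or when it will occur. The point touches two of the twelve numbered secondary outcomes at one visit and leaves the primary analysis alone. The calculation does not cover the diary-based binary outcomes in weeks 13 to 16, so nothing is claimed about them.

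**What to change.** In SAP 4.4.4, analyse the change in each PAC-SYM and PAC-QOL total and subscale score with one mixed model for repeated measures. Include arm, visit (weeks 8 and 16), arm-by-visit, baseline score and an unstructured covariance, and use every randomised patient with any post-baseline score. Report the arm difference and 95% confidence interval at each visit, as SAP 4.4.1 already asks for secondary outcomes. Label any visit-wise t-test or Wilcoxon test as available-case. Align Protocol 8.1 with the SAP by tying repeated measures analysis to these outcomes.

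State the limits beside the model: it relies on missing at random given the week-8 score, and it cannot recover patients lost before week 8. A sensitivity analysis under missing not at random would be a sensible companion, since loss through disease progression or death may break that assumption.

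The cost is SAP wording and standard SAS code, with no new visits or data. The small downside is one model per score in place of a t-test.
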